3.2.5 Data Management for WP1a

Consent will be taken and observational and interview data will be collected by researcher(s) from the co-ordinating study team or local site research team. The researcher from the co-ordinating study team will also collect contextual information.

Audio recordings will be transcribed and anonymised. Names and contact details of participants will be recorded on a separate database and stored in a locked filing cabinet. Audio recordings will be transferred from site to the university securely using encryption either on the audio recorder, or by downloading the recording to an encrypted laptop. The recordings will be transferred to secure university servers for secure storage and copies on the audio recorder and / or laptop deleted. Transfer to any transcription services will be done via a secure system and according to WCTU data transfer SOPs and a data sharing agreement. Hand written field notes will be kept in a locked filing cabinet. Field notes recorded electronically will be on an encrypted laptop while the researcher is at the site and then uploaded to secure university servers when they return to the office. Photographs will be downloaded to an encrypted laptop and transferred to secure university servers for secure storage, with the copies on the camera, phone, and / or laptop deleted. All qualitative data will be uploaded into NVivo software which will be used to assist data management.

3.2.6 Data analysis for WP1a

Data management and quality checks: Audio recordings will be transcribed and anonymised.

Names and study ID allocation for participants will be recorded separately on an electronic database and stored securely by local study teams. All qualitative data will be uploaded into NVivo software which will be used to assist data management. Coding will be undertaken by independent researchers for 30% of transcripts and any inconsistency discussed to ensure consistency.

Data coding and analysis: Data analysis will be driven by the research questions. Research questions 1-4 require a time ordered mapping of the process of decision-making. [44] Research questions 5-8 requires an interpretive approach [45] and analysis to capture the ethical dimensions. [46] We will initially code data about the decision-making process and use of Respect (or not), and for other themes relevant to the research questions and identified in the data. The decision-making process for each case will be summarised along with other relevant data (e.g. type and severity of illness) based on observation, clinician interview and patient/family interview. Comparison will be made between these different data sources and consistencies and inconsistencies noted. Comparison will then be made across cases to understand how the decision-making processes vary. The results of this analysis will then be used to inform the further interrogation of the data to answer the research questions. We will involve the project lay advisory group in data analysis and its interpretation. Our ethical analysis will take a different approach. We will follow the method of grounded moral analysis described by Dunn et al. [47] This approach initially characterizes the ethical dynamics of the practice (in this case ReSPECT decision-making) described by those participating in the practice (clinicians and patients) and exposes these to ethical analysis. Relevant ethical theories and arguments are used to make sense of the individuals' experiences and attitudes (in this case their reasoning leading to ReSPECT decisions). Emergent ethical perspectives then inform further sampling and data collection (observation and interview questions). The results of such an analysis will identify the ethical dimensions of the decision-making process and suggest the type of support clinicians may need (for example, information about legal issues, and support for coping with uncertainty or ethical dilemmas).

3.3 Study Design for Work Package 1b: Review of written records

This review of a purposive sample of patient records will seek to answer the following questions:

- 1. Is the recorded decision-making process for a ReSPECT transparent?
- 2. Is the reasoning process recorded for a ReSPECT ethically justifiable?
- 3. Are recorded decision-making processes for ReSPECTs consistent across patients and clinicians?

Our previous research identified that there is great variability in DNACPR decision-making. Uncertainty is intrinsic to most clinical decisions [48] and this was one source of variability in decision-making. Added to this was variable levels of understanding of ethical issues and of

ability to incorporate ethical considerations into clinical decision-making. [9] The wide range of health professionals across our focus groups shared a common feeling of ethical discomfort about DNACPR decision-making as it currently happens in practice. This ethical discomfort arose from difficulties in interpreting specific ethical principles such as duty of care or respect for autonomy in the particular context of resuscitation decisions, and from the need to balance conflicting duties and interests in situations of uncertainty and time constraint. One aim of ReSPECT should therefore be to support clinicians in considering the ethical reasoning underpinning ReSEPCT decisions. By embedding the DNACPR decision in a wider conversation and decision-making process about treatment options ReSPECT should prompt clinicians to involve patients and their families (respecting autonomy) and explicitly consider the overall care of the patient including the harms and benefits of a range of treatment options. It should also improve consistency of process, including reasons for decisions, across different contexts and patient populations, improving equity of care. Any evaluation of ReSPECT will need to include an assessment of whether these aims are achieved.

We are not aware of any standard instruments for evaluating the quality of ethical decisionmaking in clinical practice or for evaluating interventions to improve ethical decision-making. Studies of interventions to support ethical decision-making have usually used clinicians' views on the effect of the interventions on their practice to evaluate its impact. [49] A persuasive and pragmatic candidate for a standard by which to assess ethical decision-making is the Accountability for Reasonableness Framework (AFR) which focuses on the process of decisionmaking rather than a specific moral theory. The framework was developed in the context of resource allocation decisions in health care but can be applied to other types of health care decision. [50] The AFR has four requirements, decisions must be transparent; based on reasons stakeholders can agree are relevant; revisable in the light of new evidence and arguments; and that there should be an appeals process. Other authors have highlighted the requirement for priority setting decisions by clinicians (including ICU admissions) to be transparent (AFR requirement 1) and ethically justifiable (AFR requirements 2 and 3). [51, 52] The use of such a framework as an evaluation tool requires refining and specifying, particularly in relation to requirement 2 (relevant reasons). Assessing the quality of ethical decision-making using a framework such as AFR would ideally be achieved by direct observation of the decision-making process. However observational studies will include small numbers of clinicians and would not enable us to evaluate consistency and transparency of process across a large number of decisions. As part of a current HS&DR funded project on decision-making around admissions to ICU (HSDR 13/10/14) we are developing an evaluation tool that can be applied to the relevant section of a patient's record to assess the impact of interventions (such as a ReSPECT form) on ethical decision-making. We plan to use this tool with a sample of patient records in the six hospitals where ReSPECT evaluation will take place in addition to observation and ethical analysis of the decision-making process (WP1a).

3.3.1 Method for WP1b

We will pilot and evaluate the performance of the evaluation tool, originally developed in HSDR project 13/10/14, in a sample of records as it may need adapting to reflect the different decision-making context.

For the main analysis we will purposively sample patient records according to type of ward, ReSPECT decision choice (Focus on Life Sustaining Treatment/ Focus on Symptom Control and CPR decision) age of patient, emergency or elective admission. This sampling will allow us to focus on records where the recorded decision is more likely to be complex and ethically challenging for clinicians. We will continue sampling until we are confident that there are no new changes in the pattern of consistency, transparency, and ethical reasoning

We anticipate that the tool will provide a categorisation framework [54] for assessing transparency and ethical reasoning, and will use a configurational comparative method for assessing consistency across records.

3.3.2 Data Collection for WP1b

Sampling of records for the pilot and main study

Pilot: We will collect information about the ReSPECT process and the ReSPECT form from clinical records. We anticipate this will be up to about 20 records.

Main study: For the main analysis an NHS researcher will purposively sample patient records according to type of ward, ReSPECT decision choice, age of patient, emergency or elective admission using a sampling frame developed form the pilot sample. This sampling will allow us to focus on records where the recorded decision is more likely to be complex and ethically challenging for clinicians. An initial sample of twenty records will be selected from the first participating Trust and analysis of these records will inform further sampling at the next Trust with analysis and sampling continuing in an iterative process across all six participating Trusts until we are confident that there are no new changes in the pattern of consistency, transparency, and ethical reasoning.

Data collection for both pilot and main studies: For each set of records an NHS researcher will identify the section of the records relating to the discussion about ReSPECT and any decision made, and will copy data from this section of the record, and the ReSPECT form, having removed any patient identifiers such as name, address and NHS number. The pseudo-anonymous records will then be transferred to the research team for analysis.

3.3.3 Data Analysis for WP1b

Using the developed and tested assessment tool, we will categorise each clinical record copied according to the degree to which our criteria of transparency and ethical justification are met. Our database will include the category for each clinical record and supporting data - usually

one or two sentences from the clinical record or ReSPECT form. We will describe our findings using descriptive statistics. Consistency of decision-making will be assessed through configurational comparative methods. [54, 55] This involves the comparison of configurations of attributes of cases and their supporting data. The criteria used for each categorisation of transparency and ethical reasoning will form the attributes. Comparative analysis will be undertaken comparing each case with each other case. The comparative analysis will be undertaken independently by two analysis teams and the results compared and discussed. We will continue collecting data until no further change in the level of consistency is identified.

3.3.4 Data management for WP1b

Patient records selected for WP1b will have the relevant sections copied and be anonymsied by NHS research staff before secure transfer from site to the University of Warwick in accordance with Warwick CTU SOPs.

4. WORK PACKAGE 2

4.1 Study Design

4.1.1 Objective

To quantify the effect of the introduction of ReSPECT on frequency of and outcomes from, inhospital resuscitation attempts.

4.1.2 Rationale

A key concern of patients and relatives who contacted an end-of-life support line during our scoping review was that they would be subjected to resuscitation when it had little to no chance of success. [9] The National Confidential Enquiry into Patient Outcomes and Death (NCEPOD) report identified that resuscitation decisions were often not considered in patients admitted to hospital. [6] A key reason for this was their binary nature (for resuscitation or DNACPR) which does not allow decisions to be contextualised with other treatments. This meant that a large proportion of resuscitation attempts were undertaken in those where the NCEPOD reviewers considered a DNACPR decision should have been made prior to the cardiac arrest. These findings are consistent with data from National Cardiac Arrest Audit (NCAA) (2015-16) indicates that 6.5% of resuscitation attempts were terminated after arrival of the resuscitation team as they considered it was futile to continue.

We hypothesise that if the ReSPECT process is successful in allowing resuscitation decisions to be contextualised to overall treatment plans, the proportion of resuscitation attempts terminated by the resuscitation team as they consider resuscitation as futile will decline, the total number of resuscitation attempts will reduce and the proportion of patients, on whom CPR is attempted, surviving to go home from hospital (and their functional status) will improve.

4.2 Recruitment for WP2

Work package 2 will involve the use of anonymised data from the NCAA.

4.2.1 Withdrawals and Exclusions for WP2

WP2 is using routinely collected anonymised audit data form NCAA, so any concerns patients had about their anonymised information being included in the audit, should have been addressed by the organisation collecting the data at the time. Withdrawal will not be possible from the anonymised audit data provided to the study team.

4.3 Data Collection for WP2

NCAA collects data on hospital characteristics and individual patient demographic, resuscitation process and outcome variables for patients who sustain an in-hospital cardiac arrest and receive resuscitation by the hospital resuscitation team (or equivalent). Standardised case identification methods, data definitions, online and manual data validation ensures consistent, high quality data are collected. The NCAA Steering Committee has approved this study and for us to access the data. A sample of data will be transferred to allow the development and testing of statistical code before the final data transfer of the complete anonymised NCAA data set.

Our national audit (2014) indicates that approximately 80% of Acute NHS Trusts use the national DNACPR form (or a modified version) for making resuscitation decisions with the remainder using a system similar to the planned ReSPECT process. Although the new ReSPECT form and supporting documentation will be made available nationally in 2017, the time taken to incorporate into local Trust policies is likely to be variable. To establish baseline systems and time of change to ReSPECT we will contact the NCAA contact at each participating hospital at the start of the study and annually thereafter. The initial survey will establish (i) what system is currently in use at that Trust and how long it been in use (ii) when training for ReSPECT started (iii) when ReSPECT were first implemented (iv) when the entire organisation had adopted the ReSPECT form (v) proportion of patients who have a ReSPECT decision. Freedom of Information request will be made to each hospital, to gain as near complete information as possible in the final year of the study, since the initial survey did not yield a sufficient response rate to enable accurate analysis of the NCAA audit data.

Centres which switch from using a system of DNACPR decisions to ReSPECT between three and nine months of the launch of the national form will form the focus for the interrupted time series analysis. It is possible that some Acute NHS Hospital Trusts will not adopt the ReSPECT form or adoption may be very delayed. In this event such sites will be reported separately as observed counterfactual information.

Work package 2 will also involve an annual survey of acute Hospitals participating in NCAA to establish whether they have or intend to start using the ReSPECT process or not. A member of NHS staff, usually a Resuscitation Officer, responsible for the NCAA data will be asked to

complete the questionnaire.

4.3.1 Outcome measures

Primary: Proportion of resuscitation attempts that are terminated due to futility

Secondary:

- (i) Number of in-hospital cardiac arrests attended by the resuscitation team per one thousand admissions
- (ii) Patient status at team arrival (dead resuscitation stopped; resuscitation ongoing; ROSC achieved before team arrival; deteriorating (not yet arrested))
- (iii) Proportion of resuscitation attempts that are terminated due to presence of a DNACPR (this represents a failure of implementation)
- (iv) Vital status at hospital discharge (alive or dead)
- (v) Proportion of shockable arrhythmic cardiac arrests
- (vi) Cerebral Performance Category at discharge
- (vii) Proportion of cardiac arrests to total number of hospital deaths

4.4 Data Management for WP2

WP 2- sites will be identified by a study number only, the data will be sent securely from NCAA in an anonymised format, in accordance with WCTU SOPs and a data sharing agreement between ICNARC, NCAA and the University of Warwick.

The survey to assess use of ReSPECT will be conducted via an electronic survey tool, the sites will have the same study number as the NCAA audit data to allow linkage. The person completing the survey (the person who completes the NCAA audit) will be sent the link to the survey by NCAA and asked to enter their site ID number and/or Hospital name, depending on feasibility. The survey software will be selected or developed by the WCTU programming team to ensure it is secure. If the Hospital name is used NCAA will link the survey data set to their NCAA set to ensure anonymity of the NCAA data set by preventing the co-ordinating study team holding both the name of a hospital and its study ID. NCAA will similarly be asked to link information provided through Freedom of Information Requests to the audit data.

4.5 Data Analysis for WP2

4.5.1 Statistical Methods

We will use undertake an interrupted time-series analyses to investigate the impact of ReSPECT implementation on key outcomes in the National Cardiac Arrest Audit, in particular, the proportion of resuscitation attempts that are terminated due to futility. In an interrupted time series, the outcome is observed over multiple equally spaced time periods before and after an intervention that is expected to change either its level or trend. A linear model is fitted to the series of outcomes observed prior to the intervention and another to the period following the

intervention (optionally with the period during which the intervention is being rolled out omitted). These two regression lines are then compared as regards slope (trend) and intercept (level). The counterfactual information for the post-intervention period may be predicted from the model for the pre-implementation period or obtained from observation of the same outcome in groups that are not implementing the intervention. A key advantage of Interrupted time series analysis is that it utilises aggregated rather than individual data (hence we can use existing audit data) and accounts for trends in observed outcomes prior to the intervention.

A statistical analysis plan will be created and approved before the interrupted time series analysis is undertaken.

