4.5.2 Analysis

We will use interrupted time-series analyses (ITS) to investigate the impact of Respect implementation on key outcomes in the National Cardiac Arrest Audit, in particular, the proportion of resuscitation attempts that are terminated due to futility. The primary analysis will be a comparison of the group implementing the new ReSPECT form within three to nine months of the national implementation pre- and post-implementation. We anticipate that a period of between three and six months (depending on the speed at which the pilot/phase one is implemented) will need to be omitted from the data used for the interrupted time series analysis in order to ensure comparison of clean pre- and post- intervention periods. This analysis will compare predicted outcomes based on the model fitted to data from the pre-implementation period (i.e. we assume that the trend observed in the pre-implementation period is continued post implementation to estimate outcomes in the post- implementation time period, which is equivalent to assuming the new ReSPECT forms have no effect). As a secondary analysis we will examine actual (contemporaneous) outcomes in hospitals intending to keep using the old DNACPR forms.

197 hospitals contribute data to the NCAA programme in the UK and we will be able to obtain monthly data. By the time we come to perform the ITS analysis we will have at least 2 years (but possibly up to 5 years) of full NCAA data from the pre- implementation period and 1-2 years post-implementation. We will therefore have a minimum of 8 time points in each of the pre- and post- intervention time periods, as required for best performance of the ITS method.

The primary analysis will be performed using the ITSA command within Stata 13 with the Cumby-Huizinga test used to test for autocorrelation and determine the autocorrelation structure (identify the appropriate lag). The regression models will be calculated with Newey-West standard errors to deal with the autocorrelation and possible heteroscedasticity. Estimates of the model parameters (as appropriate) will be reported with associated 95% confidence intervals. Estimates of the trend in outcome during the post intervention period will also be reported with associated 95% confidence intervals. The results will also be presented graphically with observed and fitted data from the pre- and post-intervention periods plotted over time (quarterly) to illustrate the model fit and parameters estimated, with

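### The interrupted time series as specified has no seasonal term and may rest on one post-implementation year, so an annual cycle can be read as a level or slope change

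*Protocol*

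**What the plan says.** Protocol section 4.5.1 sets out the model: "A linear model is fitted to the series of outcomes observed prior to the intervention and another to the period following" the intervention, with the two lines compared on slope and intercept. Section 4.5.2 names the ITSA command, a Cumby-Huizinga test to choose the lag, and the error structure: "The regression models will be calculated with Newey-West standard errors to deal with the autocorrelation and possible heteroscedasticity". It treats the continued pre-implementation line as what would be seen if ReSPECT had no effect.

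On the time axis, section 4.5.2 says of the data that "we will be able to obtain monthly data" and expects "at least 2 years (but possibly up to 5 years) of full NCAA data from the pre- implementation period and 1-2 years post-implementation". Of the roll-out gap to be left out it says "We anticipate that a period of between three and six months". The study summary in section 2 instead gives two years on each side.

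The analysed hospitals are those switching three to nine months after the national launch (sections 4.3 and 4.5.2). The sensitivity analyses vary the length of the omitted period and look at subgroups. The same approach is reused for survival to discharge, attempts stopped because of a DNACPR, and shockable arrests. Hospitals keeping the old forms are a secondary analysis. Season, month of year and harmonic terms are not mentioned.

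**The concern.** A straight line continued forward is the right no-effect prediction only if the outcome has no recurring within-year pattern. If it has one, the two fitted lines absorb part of it, and that part is reported as an effect of ReSPECT or masks one. The short post-implementation segment is the most exposed, because a line fitted to a single cycle can tilt strongly depending on where in the year it starts.

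The protocol's safeguards do not address this. Newey-West errors handle serial correlation in the residuals and leave the coefficients as they are. Varying the omitted period moves the start of the post segment through the year, so the seasonal artefact moves with it. A change in the estimate could then be put down to implementation timing when it comes from season. At stake are the primary outcome and the secondary outcomes analysed in the same way.

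**Working it through.** **Inputs from the protocol.** Pre segment 24 to 60 months, post segment 12 to 24 months, omitted period 3 to 6 months (section 4.5.2); 24 months each side (section 2); baseline futility proportion 6.5% (section 4.1.2); adoption window 3 to 9 months (sections 4.3 and 4.5.2). **Not in the protocol:** the seasonal amplitude A and the number of attempts per month. Both are assumed where used.

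**Step 1: the plan's own figure and the time unit.** Section 4.5.2 claims at least 8 points in each segment. Monthly: 24 before and 12 after, so the claim holds. Quarterly: 24/3 = 8 before but 12/3 = 4 after, so it fails with one post year. Monthly is therefore the consistent reading, although the unit is not stated outright and the plots are to be quarterly.

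**Step 2: projection.** Let the outcome be a pure cycle with no true effect, y(t) = A·cos(2πt/12 + φ). Fit by least squares on X = [1, t, D, D·(t − t0)], where D = 1 after the omitted period and t0 is the first post month. The spurious estimates are b = (X′X)⁻¹X′y. The third element is the level change; the fourth, times 12, is the slope change per year. The largest absolute value over φ is:

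| Pre / omitted / post (months) | Level | Slope per year |
|---|---|---|
| 24 / 3 / 12 | 1.09A | 2.00A |
| 24 / 6 / 12 | 0.15A | 2.43A |
| 24 / 3 / 18 | 0.78A | 0.31A |
| 24 / 6 / 18 | 0.55A | 0.52A |
| 24 / 3 / 24 | 0.78A | 0.68A |
| 24 / 6 / 24 | 0.28A | 0.97A |
| 60 / 3 / 12 | 0.92A | 1.95A |
| 60 / 6 / 24 | 0.23A | 0.56A |

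Whole-year segments (24/12, 24/24) are biased. A longer pre-period does not rescue a one-year post-period.

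**Step 3: the omitted-period sensitivity analysis.** For illustration, assume a January peak, an omitted period starting in April, 24 months before and 12 after. A 3-month gap gives level −0.83A and slope +0.04A per year. A 6-month gap gives level +0.14A and slope −2.35A per year. The same artefact turns from a drop in level into a falling slope.

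**Step 4: absolute size under an assumed amplitude.** A = 5% to 10% of 6.5% = 0.33 to 0.65 points.
- One post year: level up to 1.09 × 0.33 = 0.36 to 1.09 × 0.65 = 0.71 points; slope up to 2.43 × 0.33 = 0.80 to 2.43 × 0.65 = 1.58 points per year.
- Two post years: level up to 0.78 × 0.33 = 0.26 to 0.78 × 0.65 = 0.51 points; slope up to 0.97 × 0.33 = 0.32 to 0.97 × 0.65 = 0.63 points per year.

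**Step 5: alignment.** If each hospital is aligned on its own start date and starts are spread evenly over months 3 to 9, the pooled cycle shrinks by |(1/7)·Σ exp(2πik/12)|, k = 0 to 6, which is 0.53. Every figure above is then multiplied by 0.53.

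**Step 6: false positives.** These are null simulations with binomial monthly proportions around 6.5%, an assumed 500 attempts per month, Newey-West lag 1, 500 runs, and the phase with the largest level artefact. At 24/6/12 the rate of significant slope changes is 0.12 with no season, 0.36 at A = 0.65 points and 0.64 at A = 1.3 points (20% of 6.5%). At A = 1.3, lengthening the lag to 12 gives 0.89 (300 runs), and adding a harmonic pair gives 0.13. At 24/3/24 and 24/6/18 there is no material inflation.

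**Step 7: the remedy.** Adding cos(2πt/12) and sin(2πt/12) to X brings the spurious level and slope to zero within rounding in all 18 layouts tried (pre 24/36/60, gap 3/6, post 12/18/24). Under independent errors the standard error rises by 0-7% for level and 0-19% for slope. The largest increases are 7% for level at 24/3/12 and 19% for slope at 24/6/12.

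**The case against.** **It belongs in the analysis plan.** Section 4.5.1 promises one before the analysis, its two-line sentence sits in a general explanation of the method, and nothing excludes covariates. This stands in part: a reader might infer that the trial has no seasonal adjustment at all, and the protocol alone cannot show that. But the protocol goes beyond generalities. It names the command, lag test, error structure, counterfactual and sensitivity analyses, so the point is about the primary model as written.

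**Part-year segments.** A reader might infer that the trouble comes from segments that do not cover whole years. The figures contradict this: 12 post months give the largest slope artefact and 18 post months some of the smallest. Trimming to whole years would not help.

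**No evidence of season.** The protocol reports no seasonal pattern in the futility proportion, and season in numerator and denominator may partly cancel. This stands: that a winter pattern exists, or that the result will be biased, cannot be concluded from the protocol.

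**Worst case on worst case.** The tabulated figures take the worst phase; the root-mean-square over phase is about 0.71 of them. The span in section 2 gives smaller bias, and staggered start dates could nearly halve it. All of this stands and limits the size, but none of it brings the bias to zero.

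**Contemporaneous hospitals.** Non-adopters could reveal a shared seasonal swing. True, but they are a secondary analysis and do not correct the primary estimate.

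**Conclusion.** The point holds in a conditional form. As specified, the primary model cannot tell an annual cycle from a level or slope change, Newey-West errors do not repair that, and varying the omitted period cannot separate season from implementation timing. With 24 months before and the worst phase, the artefact is 0.15A to 1.09A in level and 2.00A to 2.43A per year in slope with one post year. With two post years it is 0.28A to 0.78A and 0.68A to 0.97A per year. Alignment on each hospital's own start date would reduce A to about 0.53A.

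This rests on monthly analysis, a sinusoidal cycle, and an amplitude that the protocol does not supply; the values in points are illustrations. Exposure is greatest with a one-year post-period, which section 4.5.2 allows and section 2 does not. The change is worth making because it is cheap and protects the primary outcome.

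**What to change.** In section 4.5.2, state that the ITSA regressions are fitted to monthly data and include one annual sine/cosine pair for the primary outcome and for the secondary outcomes analysed the same way. Keep Newey-West errors for the remaining correlation. Run the omitted-period sensitivity analysis with the same terms. Reconcile the post-implementation span in section 4.5.2 with the one in section 2.

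The cost is a line of text, no new data, and two parameters on at least 24 + 12 = 36 monthly points. The loss of precision is that given in step 7 of the working, largest with one post year. One pair removes a smooth annual cycle; a more sharply peaked pattern could leave a remainder.
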